## Human Subjects

Recruitment of Subjects: Informed written consent will be obtained prior to the participation in the study and recorded in clinical documents as per Institutional stipulations. Each patient will be contacted by the principal investigator or IRB approved designees. The potential risks to participants will be minimal. The ultrasound output level used in this study is well under the current FDA safety limits for diagnostic ultrasound. No additional drugs or invasive procedures will be used in their study. The decision to participate in this study or not will not affect the treatment of patient subjects. This study involves minimal risk to the patients. All participants included in this study must have given authorization for use of their medical records in research. All subject data will be collected, reviewed, and protected according to current HIPAA regulations and as stipulated by the IRB. The data will be analyzed anonymously and all results will only be published in aggregate.

### Resources:

- Funding for the vascular boot and vascular studies (ultrasound, venous plethysmography) will be through the Vascular Center research fund.

### **Check all that apply. If none apply, leave blank:**

- This is a multisite study involving Mayo Clinic and non-Mayo Clinic sites.  
When checked, describe the research procedures/activities being conducted **only** at Mayo Clinic:
- Mayo Clinic staff will be engaged in research activity at a non-Mayo Clinic site. *When checked, provide the location and a detailed description of the Mayo Clinic research staff involvement.*
- This study is to establish and/or maintain an ongoing database or registry for research purposes only.
- The research involves contact or interaction with subjects, for example, surveys, questionnaires, observation, blood draw.

The study involves photographing, audiotaping or videotaping subjects (and guests).

### Blood Collection

If this study involves prospective blood collection by finger, heel, ear stick or venipuncture, complete the following:

**From healthy, non pregnant, adult subjects who weigh at least 110 pounds.** For a minimal risk application, the amount of blood drawn from these subjects may not exceed 550ml in an 8 week period and collection may not occur more frequently than 2 times per week.

Volume per blood draw: \_\_\_\_\_ ml

Frequency of blood draw (e.g. single draw, time(s) per week, per year, etc.) \_\_\_\_\_

**From other adults and children considering age, weight, and health of subject.** For a minimal risk application, the amount of blood drawn from these subjects may not exceed the lesser of 50 ml or 3 ml per kg in an 8 week period, and collection may not occur more frequently than 2 times per week.

Volume per blood draw: \_\_\_\_\_ ml

Frequency of blood draw (e.g. single draw, time(s) per week, per year, etc.) \_\_\_\_\_

### Review of Chart, Images, Specimens

Provide the date range for collection of data and/or specimens that will be included in your research dataset.  
*Example: 01/01/2000 to 12/31/2013 or all records through mm/dd/yyyy.*

For a retrospective chart review, enter the date range:

**Check all that apply:**

This study involves only data and/or specimens that exist at the time this application is submitted to the IRB (IRB submission date). No data or specimens will be collected beyond this date.

This study involves only data and/or specimens that will be collected after submission to the IRB.

The study involves data and/or specimens that exist at the time of submission to the IRB **and** data and/or specimens that will be collected after submission to the IRB, for example a study that includes collection of existing data and prospective collection of specimens.

Data and/or specimens used in this study are collected under another IRB protocol. *When checked, provide the IRB number(s) from which the research material will be obtained. When appropriate, check the box below to attest that subjects have provided consent for future use of their data and/or specimens, as described in this protocol.*

IRB Number/s - Data Only: \_\_\_\_\_

IRB Number/s - Specimens Only: \_\_\_\_\_

IRB Number/s - Data and Specimens: \_\_\_\_\_

Note: When subjects provided consent for use of their data and/or specimens, as described in this protocol.

Other data sources will be utilized in this study, e.g. receiving data/specimens from an external party. When checked, provide all data sources:

**Data Confidentiality, HIPAA Subject Identifiers**

Review the list of subject identifiers below and, if applicable, check the box next to each subject identifier being recorded at the time you are collecting/abstracting data/specimens for use in this study.

**Subject Identifiers:** Individually identifiable information, including demographic data, that identifies the individual or for which there is reasonable basis to believe it can be used to identify the individual. NOTE: Identifiers apply to subjects enrolled in your study and to the subject’s relatives, household members, employers, etc.

**Internal** refers to subject identifiers that will be included in the dataset maintained by the study team.

**External** refers to subject identifiers that will be shared with persons outside of the immediate study team, for example, sent to an external collaborator or shared with a national registry.

SUBJECT IDENTIFIERS Check all that apply	INTERNAL IDENTIFIER	EXTERNAL IDENTIFIER
Name	X	
Social Security number		
Medical record/patient registration number, lab accession, specimen or radiologic image number	X	
Study number, subject ID, or any other unique identifying number, characteristic or code that can be used to link the identity of the subject to the data	X	
Dates: All elements of dates [month, day, and year] directly related to an individual. Their birth date, date of death, date of diagnosis, etc.	X	

Note: Recording a year only is not a unique identifier.		
Medical device identifiers and serial numbers		
Biometric identifiers, including finger and voice prints, full face photographic images and any comparable images		
Web Universal Resource Locators (URLs), Internet Protocol (IP) address numbers, email address		
Street address, city, county, precinct, zip code, and their equivalent geocodes	X	
Phone or fax numbers	X	
Account, member, certificate or professional license numbers, health beneficiary numbers		
Vehicle identifiers and serial numbers, including license plate numbers		
If None of the above identifiers will be recorded or maintained in the dataset and/or sent outside of the study team, please check "None".	 None	 None

**Statistical Information**

*Note: Power analyses and study endpoints are not needed for a pilot or feasibility studies.*

No statistical information.

**Statistical Considerations**

**Data Analysis Plan:**

This is a pilot study including 30 volunteers. Sample size cannot be calculated statistically due to lack of prior studies in the literature for those with DVT and use of warming boot. We will recruit up to 30 subjects who have valid measurements as described in the Data Analysis plan.

The ultrasound measurements (elastography) will be assessed for validity using data analysis techniques and to examine the visualization of the venous wall to see if we can quantify the thrombosis.

All statistical tests will be 2-tailed at a significance level of  $P < 0.05$ . Demographic and physical characteristics laboratory values and comorbid conditions will be presented as mean  $\pm$  standard deviation for continuous variables and as frequencies and percentages for categorical variables. Counts and percentages will be presented for categorical variables, while means  $\pm$  standard deviations and 95% confidence intervals will describe continuous variables for which normality assumptions are met. If the distribution of a continuous parameter is skewed, transformations will be considered, or medians and interquartile ranges (IQR) will be presented. Continuous variables will be compared between 2 groups using unpaired t-tests. For comparison of continuous variables in  $\geq 3$  groups, one-way analysis of variance (ANOVA) followed by a Scheffé test may be performed. Frequencies will be compared using Chi square analysis. The correlation between 2 continuous variables will be determined using a linear regression analysis. Cox proportional hazards regression will be used to estimate the

association between thrombosis and short-term and long-term outcomes. Logistic regression will be used to estimate the association between thrombosis and binary outcomes. Adjustment for potential confounders will be accomplished through, either, covariance regression modeling, propensity score stratification, or propensity matching, according to the discretion of the statistical analyst. Statistical analyses will be performed using SAS and/or R software.

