### **Secondary Objectives**

1. Determine if early vascular boot warming plus standard anticoagulation (after 24 hours of anticoagulation therapy from time of diagnosis) is a safe intervention after diagnosis of acute DVT±PE.
2. Determine if vascular boot warming plus standard anticoagulation improves or accelerates the resolution of the clot among those with DVT±PE.
3. Determine if vascular boot warming plus standard anticoagulation improve the venous functional study measures of calf pump ejection fraction, VFR, PDR T90, and overall venous performance score.
4. Determine whether a vascular boot warming plus standard anticoagulation can improve the quality of life in patients with venous insufficiency or previous history of deep vein thrombosis of the lower extremity ± PE.
5. Identify difference in activity level between those who underwent a vascular boot warming program/activity plus standard anticoagulation versus standard anticoagulation only.
6. Analyze whether shear wave elastography will provide a more accurate and reliable method to assess the age of thrombosis and better quantification of thrombosis resolution.
7. Collect natural history data of post-thrombotic syndrome.

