### **Study Rationale Innovation and significance:**

Warming of the lower extremity enhances blood flow in the treatment of superficial vein thrombosis and has been well established. However, the effect of vascular boot warming plus standard anticoagulation on deep venous disease progression is unknown and may prove to reduce DVT with standard anticoagulation more effectively and quicker with reduced risk for PTS. To date, there is no randomized control study evaluating the effect of vascular boot warming plus standard anticoagulation in venous insufficiency. We hypothesize that the combination of vascular boot warming and standard anticoagulation will result in improvement in calf muscle pump function, thus improvement in venous physiology and quicker resolution of DVT and associated clinical symptomatology of post thrombotic syndrome. Ultrasonography with shear wave elastography imaging is a novel ultrasound technology that potentially can quantify and assess thrombosis age, evolution of thrombosis, and risk of detachment. These evaluations can be readily performed in the patient's examination room on a single ultrasound system. The overall anticipated results of our research proposal are to demonstrate that: 1) DVT may resolve more effectively with a vascular boot through warming evaluated by standard 2-D ultrasonography with compression (standard therapy); 2) shear wave elastography is a feasible diagnostic tool in those with lower extremity thrombosis; 3) shear wave elastography can provide a more accurate and reliable method to assess the age of thrombosis and better quantification of thrombosis resolution while assessing the natural history, progression, and risk of detachment; 4) this technology can readily be incorporated into the daily workflow to improve diagnostic and prognostic value for detection of DVT and resolution [It has been estimated that the average image acquisition time to be added to a standard ultrasound study is minimal (7-10 minutes for shear wave elastography imaging) 5) these techniques can improve prediction of complications among those with DVT and; 6) these techniques can help decrease the number of age indeterminate thrombus that may result in unnecessary treatment with anticoagulation and its associated risks.

**Subject Information** – charts, records, images, or specimens are considered ‘subjects’

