*Target accrual is the proposed number of subjects to be included in your study at your site. “Subjects” may include Mayo Clinic charts, records, or specimens, **and/or** charts, records, or specimens received at Mayo Clinic from external sources for collaborating analysis by the investigator under this IRB application:*

**Target accrual:** 30 patients (15 patients with vascular boot vs 15 patients without vascular boot)

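### Plethysmography has a pre-randomisation baseline, but the plan names an unpaired t-test without saying on what value; a pre-specified baseline-adjusted analysis would usually be more precise

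*Combined protocol and SAP*

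**What the plan says.** Plethysmography carries real weight in this protocol. The Study Rationale states: "We hypothesize that the combination of vascular boot warming and standard anticoagulation will result in improvement in calf muscle pump function". Secondary objective 3 asks whether the boot can "improve the venous functional study measures of calf pump ejection fraction, VFR, PDR T90, and overall venous performance score". Secondary endpoint i lists four parameters: ejection fraction, VFR, PDR T90 and EDV T90.

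Plethysmography is item 1 of the baseline studies. The text then says that the patient is randomised, so the baseline value precedes allocation. Under Follow up data it is repeated at 3 months in both groups.

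On analysis, the Data Analysis Plan gives three relevant statements:

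- "Continuous variables will be compared between 2 groups using unpaired t-tests".
- "If the distribution of a continuous parameter is skewed, transformations will be considered", with medians and interquartile ranges as the alternative.
- Adjustment for potential confounders is by "covariance regression modeling, propensity score stratification, or propensity matching, according to the discretion of the statistical analyst".

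The baseline value of the outcome is not named as a covariate anywhere.

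**The concern.** Two things are left open. The first is the variable. Endpoint i is worded as improvement, which suggests change from baseline, but the plan never says that change rather than the 3-month value goes into the t-test. These are different analyses with different precision. Which is better depends on the correlation between baseline and 3 months and on the ratio of the two SDs.

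The second is the use of the baseline. With 30 patients and no plan to recruit more, a baseline already collected is a nearly free source of precision. The plan allows it to be used through covariance regression but does not commit to it. It lists that option beside propensity stratification and matching, which address confounding that randomisation has already dealt with in the arm comparison.

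At stake is the width of the confidence interval for the boot effect on calf pump function.

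**Working it through.** **Inputs from the documents.** Total n = 30, 15 per arm (Target accrual). Tests are two-sided at 5% (Data Analysis Plan). No effect size, SD or power is given, so there is no figure of the plan's own to reproduce.

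**Assumed inputs.** Correlation between baseline and 3-month values, rho = 0.3, 0.5, 0.7. SD ratio k = baseline SD / 3-month SD = 1, 1.5, 2/3. Approximately normal data, complete on 30 patients.

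**Formulas**, as variance of the arm difference relative to a t-test on the 3-month value (= 1):

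- t-test on change: 1 + k² − 2·rho·k
- ANCOVA: (1 − rho²)(n − 3)/(n − 4) = (1 − rho²) × 27/26. The last factor is the small-sample cost of estimating the slope.

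**Example**, rho = 0.5, k = 1: change = 1 + 1 − 1 = 1.00; ANCOVA = 0.75 × 27/26 = 0.779.

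| rho | ANCOVA v 3-month value | v change, k = 1 | v change, k = 1.5 | v change, k = 2/3 |
|---|---|---|---|---|
| 0.3 | 0.945 | 0.675 | 0.402 | 0.905 |
| 0.5 | 0.779 | 0.779 | 0.445 | 1.001 |
| 0.7 | 0.530 | 0.883 | 0.461 | 1.036 |

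**Where ANCOVA loses.**

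- Against the 3-month value: (1 − rho²) × 27/26 > 1 when rho < √(1/27) = 0.19.
- Against change, k = 1: the ratio is (1 + rho)/2 × 27/26, which exceeds 1 when rho > 25/27 = 0.93.
- Against change, k = 2/3: solving (1 − rho²) × 27/26 = 13/9 − 4·rho/3 gives rho = 0.50 and 0.79; ANCOVA loses between them.
- Largest loss: 1 + k² − 2·rho·k = (1 − rho²) + (k − rho)², so the ratio to change never exceeds 27/26 = 1.038. The ratio to the 3-month value has the same ceiling, reached at rho = 0.

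**In interval terms.** For a t-test on the 3-month value the 95% CI half-width is 2.048 × √(2/15) = 0.748 SD. For ANCOVA at rho = 0.5 it is 2.052 × √(2/15 × 0.779) = 0.661 SD, about 12% narrower.

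**Detectable difference** at 80% power (a benchmark; the plan sets no power), from the noncentral t with 28 df for the t-tests and 27 df for ANCOVA, in 3-month SD units with k = 1:

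| rho | t-test, 3-month value | t-test, change | ANCOVA |
|---|---|---|---|
| 0.3 | 1.06 | 1.25 | 1.03 |
| 0.5 | 1.06 | 1.06 | 0.94 |
| 0.7 | 1.06 | 0.82 | 0.77 |

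**Checks.** Simulation of 40,000 trials per setting gave ANCOVA variance ratios of 0.947, 0.782 and 0.532 against the 3-month value at rho 0.3, 0.5 and 0.7, in line with the formula. False-positive rates under the null were 4.8–5.3% for all three methods. With 24 completers (assumed) the ratios are 0.956, 0.787 and 0.536, and the largest loss is 21/20 = 1.05.

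**The case against.** The strongest case against is that this is a preference between valid methods. Each holds its 5% error rate, covariance regression is already on the plan's list, and the endpoint wording makes change a reasonable reading. The gain also rests on a correlation that the documents do not give. Baseline is taken in the acute phase, within a day or two of diagnosis, and the outcome comes 3 months later. Over that interval the Background describes widely varying clot resolution. The correlation could therefore be low, and at 0.3 the detectable difference only moves from 1.06 to 1.03 SD. Finally, this is a secondary endpoint in a pilot, and the template note says that pilots need no power analysis.

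Most of this stands, and it limits the weight of the point. It does not remove it. The plan still tests at P < 0.05, the variable is still unnamed, and the recommendation does not depend on knowing the correlation, because the possible loss is about 4% and the possible gain is much larger.

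A reader might infer several stronger things that the documents do not support:

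- *ANCOVA always wins.* It does not; the ranges where it loses are given above.
- *The plan rules out baseline adjustment.* It permits it, at the analyst's discretion.
- *The plan matches randomised patients on propensity scores.* The adjustment sentence follows models such as "Logistic regression will be used to estimate the association between thrombosis and binary outcomes" and most naturally serves those. It merely does not exclude the arm comparison.
- *The primary ultrasound endpoint is affected.* Nothing here bears on its test, for or against.

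**Conclusion.** The point holds as a minor, inexpensive improvement to secondary endpoint i. The gap is a lack of pre-specification, both of the variable tested and of the use of baseline; it is not an invalid test. For mid-range correlations with equal SDs, ANCOVA improves on both t-tests. Elsewhere it is at worst about 4% less efficient in variance than the better of them (about 5% with 24 completers). The figures assume roughly normal data and a roughly linear relation between baseline and 3-month values. The correlations and SD ratios are illustrative, not estimates for this population.

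**What to change.** In the Data Analysis Plan:

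1. For each plethysmography parameter in endpoint i, replace the unpaired t-test with ANCOVA of the 3-month value on randomised arm plus the baseline value of the same parameter (same leg, if recorded by leg). Include all randomised patients with follow-up data, analysed as assigned. Report the adjusted difference with its 95% CI. If the rule for skewed variables leads to a transformation, apply it to baseline and follow-up alike.
2. As a minor clarification, state that propensity stratification and matching are confined to the exploratory models with thrombosis as the exposure, and are not used for the randomised arm comparison.

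Calf circumference is left out because it is not a listed endpoint.

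The cost is two or three sentences, with no new visits, measurements or patients. The statistical price is one degree of freedom, the small possible variance penalty, and reliance on approximate linearity, which a plot of 3-month against baseline values by arm can check.

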## **Background:**

Venous thromboembolism (VTE) is a major public health problem with over 500,000 incident or recurrent VTE events occur in the US annually. Survival after VTE is reduced, especially after pulmonary embolism (PE). The incidence of VTE in Olmsted County, MN increased by ~5% per decade over the 30-year period, 1981-2010. Anticoagulation for VTE has been the mainstay treatment with little advancement. Unfortunately, acute and chronic venous disorders are extremely common in those that experience VTE. Post-thrombotic syndrome (PTS) is one of the dreaded long-term complications of deep venous thrombosis (DVT). It's been estimated that 1 to 3 of 1000 people in general population is affected by DVT and 25% to 50% patients of patients with DVT develop PTS. The manifestations of PTS can vary from minor leg swelling at the end of the day to severe complications of debilitating limb pain, intractable edema, and leg ulcerations requiring extensive nursing and medical care. It can reduce the patient's quality of life in addition to being a significant financial burden. It is estimated that annually we spend over a billion dollars (up to 2% of the total healthcare budget in all Western countries) on the treatment of chronic wounds. There are still huge gaps in understanding the underlying mechanism and progression of the condition.

Expedient resolution of thrombosis may have a significant impact on PTS. Resolution and recanalization of venous thrombosis generally begins within 1 week of the acute episode. Studies have shown that at least 5% of thrombosed venous segments completely clear within 1 week and 16% to 51% of the cases

resolved within 6 months. Killewich et al demonstrated thrombus regression was evident at 1 to 2 weeks and progressed such that only 26% of residual thrombus remained at 24 to 36 weeks. Complete resolution of thrombus occurred in 10 of 18 patients (56%) who completed the 9-month study.

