**Ultrasound Measurements and Criteria:**

The criteria for complete occlusion (occlusive) were absence of flow with distal augmentation and incompressibility of the vein. Minimal clot will be defined by wall thickening, webbing, etc. Partial recanalization will be defined by >50% or <50% normal or diminished flow with distal augmentation and partial incompressibility of the vein. Complete recanalization (resolved or no clot) will be defined by spontaneous phasic flow and a completely compressible vein and no residual clot (see Table 2).

Table 2.0

Site	No Residual Clot	Minimal Clot (wall thickening, webbing, etc)	Recanalized >50%	Recanalized <50%	Near Occlusive	No Change	Worse Or Extension
External Iliac (EIV); if evaluated							

Common femoral (CFV)							
Femoral- Upper (FV)							
Femoral - Middle							
Femoral - Lower							
Deep femoral (DFV)							
Popliteal (PV)							
Posterior tibial (PT-calf)							
Gastrocnemius (G-calf)							
Peroneal (P-calf)							
Soleal (S-calf)							
Total							

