## **Endpoints**

### **Primary:**

Early resolution of the DVT±PE as measured by the ultrasound. Partial recanalization will be defined by normal or diminished flow with distal augmentation and partial incompressibility of the vein (>50% or <50%). Complete recanalization will be defined by spontaneous phasic flow and a completely compressible vein.

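### The ultrasound outcome is an essentially ordered clot grade, but the only test named for frequencies is chi-square; at 15 v 15 an unordered chi-square gives up roughly two-fifths of the power of an ordered test

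*Combined protocol and SAP*

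**What the plan says.** The primary endpoint (Endpoints, Primary) is "Early resolution of the DVT±PE as measured by the ultrasound". The same paragraph defines an intermediate state: "Partial recanalization will be defined by normal or diminished flow with distal augmentation and partial incompressibility of the vein (>50% or <50"%).

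Ultrasound Measurements and Criteria defines the best state: "Complete recanalization (resolved or no clot) will be defined by spontaneous phasic flow and a completely compressible vein and no residual clot". Table 2 there has seven columns for each of up to 11 vein sites. Five are states in a natural order: no residual clot, minimal clot, more than 50% recanalized, less than 50% recanalized, near occlusive. The other two, No Change and Worse Or Extension, describe change from an earlier scan.

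Target accrual is "30 patients (15 patients with vascular boot vs 15 patients without vascular boot"). Follow-up ultrasound is at 3 days, 10 days and 3 months.

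The Data Analysis Plan states "All statistical tests will be 2-tailed at a significance level of" P < 0.05. For categories it gives "Frequencies will be compared using Chi square analysis". It also says "Logistic regression will be used to estimate the association between thrombosis and binary outcomes". Nothing in it uses the order of a categorical outcome, and no exact test is named. It does not say which test applies to the primary endpoint, at which visit, or how the sites of one leg become one result per patient.

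**The concern.** The trial asks whether clots clear sooner with the boot, which on this scale means a shift toward better grades. A Pearson chi-square on the full table treats the grades as unlabelled categories. It spreads a one-directional shift over several degrees of freedom, and with 30 patients the table is sparse.

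Collapsing to complete resolution gives one degree of freedom but ignores movement among the other grades. That matters most on the two early scans, when few clots are expected to have cleared. The Background reports that "at least 5% of thrombosed venous segments completely clear within 1 week".

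At a fixed 30 patients, the choice of test is one of the few ways to get more information at almost no cost.

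**Working it through.** The plan gives no power or sample-size calculation, so there is no figure to reproduce.

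**Inputs from the protocol.** 15 per arm; two-sided 0.05; five ordered states in Table 2; at least 5% of segments clear at 1 week.

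**Assumed inputs.** One grade per patient, no dropout, a common odds ratio (OR) of 5 applied to every cumulative split, and three control distributions, best to worst grade:
- early scan: 5/15/25/30/25%
- even: 20% each
- about 3 months: 40/20/20/10/10%

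**Expected counts.** Thirty patients over 2 × 5 cells average 30/10 = 3.0 per cell. This is only an average. With no effect, the early split gives 15 × 0.05 = 0.75 up to 15 × 0.30 = 4.5, and the 3-month split gives 15 × 0.10 = 1.5 up to 15 × 0.40 = 6. If 5% of control patients had cleared, that is 0.75 of 15.

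**What OR 5 means for complete resolution.** Treated proportion = 5o/(1 + 5o), where o is the control odds.
- early: o = 0.05/0.95 = 0.0526, so 5% becomes 0.263/1.263 = 21%
- even: o = 0.25, so 20% becomes 1.25/2.25 = 56%
- 3 months: o = 0.40/0.60 = 0.667, so 40% becomes 3.33/4.33 = 77%

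**Simulated power at OR 5, 15 v 15.**

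| Control split | Unordered chi-square, 2 × 5 | Chi-square, complete resolution | Fisher, complete resolution | Wilcoxon |
|---|---|---|---|---|
| Early | 37% | 21% | 10% | 63% |
| Even | 38% | 53% | 35% | 64% |
| 3 months | 32% | 54% | 37% | 57% |

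Repeat runs agree within one or two percentage points.

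**Share of the Wilcoxon power lost** (1 − power/Wilcoxon power).
- Unordered chi-square: 1 − 37/63 = 41%; 1 − 38/64 = 41%; 1 − 32/57 = 44%.
- Complete resolution: 1 − 21/63 = 67%; 1 − 53/64 = 17%; 1 − 54/57 = 5%.

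**Type I error.** Wilcoxon stays at about 5%. The chi-square on complete resolution has an actual error of about 0.4-0.6% when 5% of controls clear, so on an early scan it can hardly reject.

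**Sensitivity to the number of grades and the effect** (Wilcoxon v unordered chi-square).
- 3 equal grades, OR 4: 50% v 40%, loss 20%
- 5 equal grades, OR 4: 53% v 30%, loss 43%
- 5 equal grades, OR 10: 90% v 69%, loss 23%
- 7 equal grades, OR 4: 54% v 22%, loss 59%
- The only grade split in the protocol (segments at 1 year, 60/27/13%), OR 4: 36% v 26%, loss 28%

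**Smaller effect.** At OR 3 the Wilcoxon test itself has about 32-36% power across the three splits.

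**The case against.** The strongest reply is that the plan never says chi-square will be applied to the five-level grade. A yes/no resolution endpoint, analysed by chi-square or logistic regression, fits the text equally well. That is true, and the more basic gap is that the primary analysis is unspecified. But both readings are covered above, and neither uses the order of the grades. Nor is complete resolution the only possible cut: dichotomising the early split at more than 50% recanalized or better gives about 52% power, so the two-thirds loss belongs to the complete-resolution cut on an early scan.

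A reader might infer that most of the available power is lost. The figures do not support that in general. Of the six comparisons at OR 5, only complete resolution on the early scan loses more than half. Nor is an unordered chi-square blind to shifts among the middle grades; it detects them less efficiently.

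Three further limits stand. The 5% is a floor for segments, used here as a patient proportion. One grade per patient needs a rule that the plan does not give, and two of the seven columns in Table 2 are not states on the scale. Finally, the study is a pilot that claims no power, and 30 patients is a tighter limit than the choice of test. The pilot label excuses the missing power calculation, but the plan still commits to two-sided tests at 0.05, and a better-suited test costs almost nothing.

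**Conclusion.** The concern holds in a limited form. The outcome is essentially ordered, and no test that the plan names for a categorical grade uses the order. With five grades, 15 per arm and OR 5, an unordered chi-square loses roughly two-fifths of the power of the Wilcoxon test (32-38% v 57-64%). Chi-square on complete resolution loses about two-thirds on an early scan with 5% of controls cleared (21% v 63%) and very little at 3 months (54% v 57%).

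These sizes rest on assumed grade splits, an assumed common odds ratio and one grade per patient. The loss is smaller with three grades or very large effects and larger with seven grades. An ordered test makes better use of the data but does not make the trial adequately powered for a moderate effect. The change should be made, but the trial does not fail without it.

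**What to change.** In the Data Analysis Plan:

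1. Name one early visit and one ordered grade per patient. One workable rule is the worst grade across the segments thrombosed at baseline: no residual clot, minimal clot, more than 50% recanalized, less than 50% recanalized, near occlusive or occlusive.
2. Where a segment is marked No Change or Worse Or Extension, also record the actual state of the vein at that visit, so that every patient has a place on the scale.
3. Compare arms by the Wilcoxon rank-sum test with an exact or permutation P value.
4. Report the common odds ratio from a proportional-odds model, or the probability of a better grade, with a 95% interval. For a pilot this estimate is the more useful result.
5. For sparse yes/no tables, use a mid-P or unconditional exact test. Plain Fisher would cut power further: 10% v 21%, 35% v 53% and 37% v 54% against chi-square in the three settings above.

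The cost is a few sentences, a one-line rule for the patient grade and a small clarification to the Table 2 form; no extra scans are needed. The common odds ratio assumes a similar shift at each grade, which 30 patients cannot check well; the probability of a better grade avoids that assumption.
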